Approximately 20% to 25% of the patients treated with 3.5 mg/kg as monotherapy developed transient Grade \geq 3 lymphopenia. Grade 4 lymphopenia was observed in 0.7% of patients. Overall, nearly 90% of patients recovered by the end of the trials. The remaining patients recovered during long-term follow-up without developing severe or opportunistic infections.

Herpes zoster infection is considered as an important identified risk of cladribine treatment. The observed incidence rates in the monotherapy oral cohort for herpes zoster infection were 0.86 adjusted adverse events (AEs) per 100 PY for oral cladribine 3.5 mg/kg vs. 0.20 for placebo, and for severe herpes zoster infection 0.9 vs. 0.5, respectively. The incidence of herpes zoster infection was higher during periods of Grade 3 or 4 lymphopenia compared to the time when the patients were not experiencing Grade 3 or 4 lymphopenia.

Incidence rates of the most common infections, including the most common severe infections, were similar between the placebo and the oral cladribine exposed groups, with the exception of herpes zoster infection as described above. The incidence rates for infections, in general, were 24.93 vs. 27.05 adjusted AEs per 100 PY (cladribine 3.5 mg/kg monotherapy vs. placebo), and for severe infections 0.84 vs. 0.86, respectively. There was no evidence for an increased risk of opportunistic infections in subjects treated with oral cladribine (incidence rates were 1.08 and 1.17 for oral cladribine 3.5 mg/kg monotherapy and placebo, respectively). However, tuberculosis has been defined as an important identified risk, with overall 3 cases observed in the cladribine development program. All cases were reported prior to the implementation of mandatory pre- screening for tuberculosis; no cases occurred thereafter.

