Analysis of duration of severe lymphopenia will be descriptive using Kaplan-Meier curves stratified by key prognostic factors.

Effect of prior use of immunomodulatory/ immunosuppressive agents on the occurrence of AESI

The effect of the prior use of immunomodulatory (IM) agents or immunosuppressive (IS) agents on the incidence of AESI in patients initiating oral cladribine or fingolimod will be assessed by including such variables into the Poisson regression model. A separate variable will be used for prior IM or IS agents used for treatment of other conditions than MS.

Description of sequential use of DMT after cladribine treatment in patients who experience a recurrence of the disease activity

Number and percentage of patients that experience a recurrence of the disease activity in both oral cladribine and fingolimod cohorts as well as type of DMT given after oral cladribine or fingolimod (immunosuppressive or immunomodulatory agents), such as switch to fingolimod, oral cladribine, interferons beta-1a, interferons beta-1b, natalizumab, teriflunomide, glatimater acetate, or other DMTs.

Subgroup analyses for the RRMS population

The primary analysis described above will be performed for the subset of patients with RRMS treated with oral cladribine and in all patients included in the fingolimod cohorts. This analysis will be limited to patients with available information on the clinical course of the disease at enrolment.

Exploratory analyses

Description of discontinuation

Number and percentage of patients discontinuing initial treatment (oral cladribine or fingolimod) will be computed for both cohorts, and presented together with the main reasons for discontinuation. Treatment start and discontinuation dates will be taken into account. Kaplan-Meier curves will be used to characterize time to treatment discontinuation.

Relationship between severe lymphopenia and AESI

Relationship between severe lymphopenia and AESI in the oral cladribine cohort will be further evaluated by looking at the temporal associations of the respective events.

The following 2 variables will be constructed:

- 1) Time since lymphopenia as a continuous variable
- 2) Number of lymphopenia episodes: $0, 1-2, \ge 2$.

AESI will be tabulated (number and percentage) with respect to the above variables.

In addition to quantify the temporal association between severe lymphopenia and AESI, the above variables will be added to the analysis of AESI.

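### Neither covariate fixed for the lymphopenia-AESI analysis is current Grade 3/4 status, so the during-episode association can be misstated

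*Protocol*

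**What the plan says.** Section 9.8.3, under the exploratory analyses, sets the aim: "Relationship between severe lymphopenia and AESI in the oral cladribine cohort will be further evaluated by looking at the temporal associations of the respective events". It then names two variables to be built. The first is "Time since lymphopenia as a continuous variable". The second is "Number of lymphopenia episodes", grouped as 0, 1-2 and ≥2. AESI are tabulated by both, and to quantify the temporal association "the above variables will be added to the analysis of AESI". The text does not state whether time runs from onset or from resolution, whether either variable is updated over follow-up, or what value of time a patient without an episode takes. Full methodology is left to the SAP.

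Two statements in Section 7 (Oral Cladribine) bear on the choice. On frequency: "Approximately 20% to 25% of the patients treated with 3.5 mg/kg as monotherapy developed transient Grade" ≥ 3 lymphopenia. On the link to an AESI: "The incidence of herpes zoster infection was higher during periods of Grade 3 or 4 lymphopenia" than outside such periods.

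Section 9.4.2 defines an episode from the finding of severe lymphopenia to its resolution, so both dates are planned.

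**The concern.** Section 7's evidence linking lymphopenia to higher AESI incidence is a contrast between time in Grade 3/4 and time outside it, for herpes zoster. The variables fixed for this study do not draw that contrast. If time is counted from onset, a given month of a continuing episode looks the same as that month after a short, resolved one. If time is counted from resolution, time inside an episode has no value. The count does not separate ongoing from past episodes.

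Time since lymphopenia is also undefined for anyone without an episode and for follow-up before a first episode, so its meaning depends on how it is combined with the count.

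At stake is the exploratory objective itself: whether routine-practice data show the excess infection risk during severe lymphopenia that the development programme reported for herpes zoster, and how large it is.

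**Working it through.** The protocol gives no figure for this analysis, so there is nothing to reproduce. The check has three parts.

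**1. Who has no value of time since lymphopenia.** With 20-25% developing Grade ≥3 lymphopenia (Section 7), 1 − 0.25 = 75% to 1 − 0.20 = 80% do not. Of 4,000 cladribine patients (Section 9.1.1) that is 3,000 to 3,200, if the trial rate carries over to routine practice.

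**2. Can the two variables be fitted together?** Let E(t) = 1 from the onset of a first episode and 0 before or without one. Let S(t) = years since onset, set to 0 when E(t) = 0. The model is

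log rate = a + b·E(t) + c·S(t).

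The design has full rank (3 of 3). Patients with E = 0 form the reference, and S varies only after onset. The fitted ratio s years after onset is exp(b) × exp(c)^s.

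**3. What does that model return when risk is raised only during an episode?** Poisson regression on simulated monthly person-time, 200 replicates per setting.

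- From the protocol: 4,000 patients; 4 years (the recording period for non-malignancy AESI, Section 11.4); 20% or 25% with an episode; herpes zoster at "0.86 adjusted adverse events (AEs) per 100 PY for oral cladribine 3.5 mg/kg" (Section 7), used as the rate outside episodes.
- Assumed: one episode per affected patient, onset in months 2-25, length 3, 6 or 12 months, and a true ratio of 3 or 5 during the episode and 1 otherwise.

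Median estimates (ranges are over 20% and 25% affected):

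| Episode length | True ratio | Ratio at onset, exp(b) | Factor per year, exp(c) | Ever v. never episode alone | Current-status indicator |
|---|---|---|---|---|---|
| 3 months | 3 | 1.66-1.72 | 0.75 | 1.15 | 2.87-3.03 |
| 6 months | 3 | 2.20-2.30 | 0.65-0.69 | 1.30-1.35 | 2.90-3.03 |
| 12 months | 3 | 3.38-3.45 | 0.58-0.60 | 1.71-1.74 | 3.03-3.09 |
| 3 months | 5 | 2.41-2.46 | 0.62-0.63 | 1.33-1.35 | 4.89-4.94 |
| 6 months | 5 | 3.78-3.86 | 0.50-0.51 | 1.68-1.70 | 4.86-5.05 |
| 12 months | 5 | 5.99-6.21 | 0.44-0.45 | 2.36 | 5.00-5.01 |

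The joint model fits a smooth decline to what is a step, so it is too low with short episodes and too high at onset with long ones. Example, 6-month episodes, true ratio 3, 20% affected (unrounded 2.195 and 0.685): at the end of the episode 2.195 × 0.685^0.5 = 1.82, where the truth up to that point is 3. At one year it is 2.195 × 0.685 = 1.50, where the truth is 1.

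**Precision.** Current-episode time was 1.3% to 6.3% of person-time. Over 4,000 × 4 = 16,000 PY that is about 208 to 1,008 PY. Expected events in that state range from 208 × 0.0086 × 3 ≈ 5 to 1,008 × 0.0086 × 5 ≈ 43. A single study's estimate could therefore be imprecise even with the right variable.

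**The case against.** The strongest reply is that the two variables are entered together. The 0-episode category supplies the reference group, so never-affected patients need not leave the model and setting their elapsed time to 0 does no harm. That stands. A reader might infer that 3,000-3,200 patients, with their person-time and events, drop out, or that the association cannot be estimated at all. The documents do not support either. Such a loss would occur only if undefined values were treated as missing, which the protocol does not say.

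Second, time origin, updating and coding may be left to the SAP. That also stands, and their absence is not the point. The list of variables is stated, however, and a SAP that implements it as written still has no current-status term.

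Third, the simulation generates events from current status, so that indicator is bound to recover the truth. Agreed. Its use is to show what the planned terms return if risk follows the pattern Section 7 describes for zoster. It is not evidence that risk does so.

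Fourth, current status is not the obvious exposure for malignancy, where the protocol stresses induction and latency. Elapsed time and episode count are reasonable there.

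Fifth, resolution dates rest on unscheduled blood tests. Sections 9.8.2 and 9.10 acknowledge that duration may be overestimated, and Section 9.10 says that differences in recording limit assessment of completeness in secondary-use sources. A current-versus-resolved split inherits that error, and the group with no episode to date will include untested patients. This is a real limitation of the remedy, but no reason to omit the contrast.

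**Conclusion.** The point holds in a limited form. The fixed covariates can yield an association, but not the during-episode contrast that Section 7 reports. If risk is raised mainly while lymphopenia is present, the ratio at onset from the planned terms was 1.7-3.5 for a true 3 and 2.4-6.2 for a true 5. The ever-versus-never ratio was 1.15-1.74 and 1.33-2.36 respectively. These ranges rest on the assumed episode lengths, onset times, single episodes and true ratios; they are not protocol values. The 75-80% without an episode is carried over from the trials and may differ where testing is not scheduled.

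A separate slip in the same list is certain: the categories 1-2 and ≥2 both contain two episodes.

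The analysis is exploratory, the concern applies mainly to infections, and no primary or secondary conclusion depends on it.

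**What to change.** In the exploratory analysis in Section 9.8.3:

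- Add a time-updated state for each cladribine patient: no severe lymphopenia to date (reference), current severe lymphopenia, after resolution. Sections 9.4.1 and 9.8.3 already treat drug exposure this way, with current, recent and past use and time-dependent exposure indicators.
- Define time since lymphopenia as time since resolution, nested within the third state only.
- Count episodes only up to each AESI or person-time interval, and make the categories non-overlapping.
- Tabulate AESI events and person-time by state.
- Aim the current-status contrast at infections. For malignancy keep elapsed time and episode count.

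The cost is a change of wording and some programming. Onset and resolution dates are already planned, and the secondary lymphopenia analysis in Section 9.8.3 already has to identify ongoing episodes in order to exclude that time. The downside is misclassification between current and resolved status, because blood tests are not mandated. State this as a limitation beside the results, together with the number of events in the current state.

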9.8.4 Sequence of Analyses

According to the milestones in Section 6, analyses will be performed as part of the additional pharmacovigilance activities for oral cladribine. No control of the Type I error will be implemented and comparison between oral cladribine and fingolimod cohorts will only be performed when enough data has been accumulated in light of the expected background incidence rate. Full details will be described in the SAP.

In addition, further analyses or reporting might be performed to address regulatory requirements and/or to investigate spontaneous reporting safety signals.

9.9 Quality Control

This study will be conducted according to the rules of 'Good Pharmacoepidemiology Practice' (GPP) and the 'Guideline on good pharmacovigilance practices (GVP) – Module VIII (Rev 1)' EMA/813938/2011 Rev 1.

The investigator will comply with the confidentiality policy as described in the site contract, with the requirements described in the protocol. The treating physician is ultimately responsible for the conduct of all aspects of the PASS at the local level and verifies the integrity of all data transmitted to the CRO.

Related quality control mechanisms (eg, data plausibility checks, monitoring of data) will be performed accordingly.

9.10 Limitations of the Research Methods

Selection bias

Selection bias is a distortion of evidence or data that arises from the way that patients are selected and from the completeness of outcome ascertainment (loss to follow-up). Selection bias may arise if the study sample differs substantially from the underlying target population of patients with R(R)MS in the selected countries. Patients with R(R)MS could be referred to multiple medical specialists (neurologists, ophthalmologists, urologists, cardiologists and others) and receive treatment at different types of sites (centers of excellence, university hospitals, general hospitals),

which may in turn be related to disease presentation and degree of severity. To minimize selection bias, the eligibility criteria were selected to be as broad as possible for this study population. In addition, the participating study sites with additional primary data collection will be expected to invite all consecutive eligible patients to participate and sites will enroll patients prospectively during the study period. In the countries with secondary use of data only, all eligible patients will be included during the study period.

Generalizability of results

The generalizability of results and representativeness of the sampled R(R)MS population included in the PASS will be assessed using patients' characteristics at enrolment and known information of the epidemiology of R(R)MS at the time of the report.

Since this study is conducted via secondary use of data through registries, complemented (when needed) or not with additional primary data collection, some countries were not eligible for this study. However, regarding the countries included in this study, those with among the highest MS incidence in Europe, are included, such as the Czech Republic, Finland, Denmark, France, and Norway (11, 9, 7.89, 7.6, and 7 per 100.000 person-years, respectively) (Multiple Sclerosis International Foundation 2013). Italy and Spain (as well as Turkey) are included to represent the southern countries, and those with the second and third highest incidence of tuberculosis of the Western European countries (Spain and UK with 10 and 9.9 cases of tuberculosis per 100,000 population, respectively) (World Health Organization, 2017) are included.

Information bias

Information bias is a distortion in the estimate of association between risk factor and disease that is due to systematic measurement error or misclassification of patients on 1 or more variables, either risk factor or outcome. To preventively minimize this type of bias in the current study, instructions will be provided to all neurologists/physicians in the centers participating through the databases with additional primary data collection. In the data sources with secondary use of data, the data collection is based on routine clinical practice and cannot be influenced in the context of the study.

As the study is non-interventional, only data from clinical routine practice can be obtained. Therefore, some information may be missing or unavailable. As an example, treatment discontinuation and the association of severe lymphopenia and AESIs might be difficult to assess due to low completion and/or heterogeneity of data collection for these outcomes in the participating data sources. In addition, this may be an issue when measuring the duration of lymphopenia. Given that no regular blood tests are requested per protocol, there is a risk to overestimate the duration of lymphopenia. In patients with severe lymphopenia, this risk of bias will probably be minimized as the physician would be expected to perform a closer follow-up with more frequent blood testing. For data sources with additional primary data collection, the data will be entered according to the study protocol and recoding of lymphocyte counts, when performed, is mandatory by the physician. In data sources with secondary use of data, the differences in the recording of lymphocyte counts between different MS treatments and different medical practices will limit the assessment of completeness of recording.

Furthermore, given that oral cladribine is a new drug, the treating physician might pay extra attention and evaluate the patient more frequently (higher number of clinical visits, laboratory testing, etc.), introducing a possible detection bias in comparison to patients treated with fingolimod.

Confounding by indication and/or channeling bias

Confounding by indication and/or channeling bias may result from selective prescribing of a specific medication to patients with a different clinical profile (eg, more severe disease). This bias can also arise because of differences in the contraindications and warning and precaution sections between fingolimod and oral cladribine. This will influence drug prescription and, if related to the outcome, act as a confounding factor.

Oral cladribine will be a new drug coming on the market at the start of this study. Thus, patients newly initiating oral cladribine at the very beginning of the study might be different from patients treated with fingolimod or patients who will be treated in later years (eg, with more comorbidities, lack of treatment responsiveness, particular safety profile, not stabilized with other available MS treatments). This effect is often observed when a new drug enters the market and is known as channeling bias. This effect will tend to decrease upon study course.

To address this potential bias:

- Subgroup analysis restricting the study cohorts to patients with RRMS will give insight on any potential impact of indication on the study results.
- Adjustment of outcomes for confounders and effect modifiers will minimize any differences that are due to the presence of different background risk;
- Propensity score adjustment might be used if the 2 cohorts are shown to have statistically significant key differences in characteristics at enrolment.

Limitations related to data sources

Danish data cannot leave Denmark and must be analyzed on the server of a Danish register holder. This limitation can be overcome by running the pooled analyses on the server of a Danish register holder, where a dedicated virtual server space will ensure secure data storage.

In all Nordic countries, the national healthcare registers have a lag time of 3-12 months. Thus, for example data for the anticipated final study year 2033 will be available during 2034. The study period in the Nordic countries is suggested to end 1 year earlier than for the countries using additional primary data collection, to enable holding the suggested timelines. The target study cohort sizes have been defined across all countries and thus the population sizes to be collected per individual country can be adjusted.

Missing variables

- The OFSEP database in France does not collect data on the date of diagnosis, only on the date of onset.
- Information on race of the patient will not be available.
- Availability of data on the predefined risk factors varies by data source: all variables are not currently available in any of the data sources. However, in the data sources using additional

primary data collection potential missing variables can be collected via a module specifically designed for the study purpose.

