9.4.2 Outcome Definitions

Malignancy: Any occurrence of malignant neoplasms during the study period. These will be grouped and classified by type. Malignancies will include all pathologically confirmed solid tumors (excluding non-melanoma skin cancer) and hematological malignancies, as the primary outcome for all malignancies-related analyses. Benign tumors will not be collected. The pre-defined groups are the following:

- Any malignancies excluding non-melanoma skin cancer (NMSC) (primary)
- Any malignancies including NMSC
- Solid tumors only
- Hematological tumors only

Severe infections:

The following categories will be investigated:

- Tuberculosis
- PML
- Opportunistic infections (excluding herpetic infections, tuberculosis, and PML): defined as an invasive infection caused by microorganisms that are normally non-pathogenic or rarely pathogenic in individuals with normal immune function or cause an infection of a type or severity not seen in the normal host.
- Other severe infections

All bacterial, viral, fungal, parasitic and protozoal infections that occur during the study period and regardless of the duration of infection will be recorded. The duration of infections will be the difference between start date and recovery date as reported by the treating physician. Patients may contribute for more than one episode to this analysis if, after resolution as defined, another infection occurs.

An infection will be considered severe if it leads to a significant impairment of functioning, i.e., the subject is unable to carry out usual activities. This definition includes serious and non-serious infections, in line with the definition used in the RMP of oral cladribine. An infection is considered serious if it fulfills at least one of the following seriousness criteria: results in death, is life-threatening, requires in-patient hospitalization or prolongation of existing hospitalization, results in persistent or significant disability/incapacity, is a congenital anomaly/birth defect, or is otherwise considered as medically important.

As the availability of data related to certain infections may vary among the databases, detailed operational definitions for the identification of severe and opportunistic infections in different disease coding systems used by data sources of the study will be defined in the statistical analysis plan (SAP).

Herpes zoster infections: Regardless of the severity.

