Severe lymphopenia: Any occurrence of severe lymphopenia during the study period, classified as Grade ≥ 3 . As per the Common Terminology Criteria for Adverse Events (CTCAE) (V4.03: June 14, 2010) from the National Institutes of Health, the grades of lymphopenia are defined based on laboratory test results that indicate a decrease in number of lymphocytes in a blood sample:

- Grade 3: $<500 200/\text{mm}^3$; $<0.5 0.2 \times 10^9 /\text{L}$
- Grade 4: $<200/\text{mm}^3$: $<0.2 \times 10^9/\text{L}$

Duration of severe lymphopenia: Defined as the interval from the finding of severe lymphopenia until resolution, which is achieving a CTCAE Grade 1 (less than lower limit of normal [LLN] to 0.8×10^9 /L) or normalization (above LLN). Patients may contribute for more than one episode to this analysis if, after resolution as defined, severe lymphopenia occurs. The frequency of lymphocyte counts in patients with severe lymphopenia will be described with special emphasis on the number and timing of lymphocyte counts in relation to oral cladribine dosing.

Treatment interruption: In the oral cladribine cohort, discontinuation will be further defined as stopping the treatment before completion of a treatment course. Discontinuation will be considered temporary if the patient restarts the same or the second treatment course with a delay of up to 6 months. Otherwise, it will be considered permanent. With regards to discontinuation in the fingolimod cohort, it will be considered as temporary discontinuation if the patient restarts fingolimod within 90 days after temporary discontinuation or permanent discontinuation if there are no more records of fingolimod thereafter.

Treatment discontinuation: Treatment discontinuation will be directly recorded by the treating physician and includes any permanent treatment discontinuation (excluding treatment interruption), regardless of the reason for discontinuation. Reasons and dates for discontinuation will also be captured. The treatment stop date will be used to derive the date of treatment discontinuation.

For complete and accurate information, for each of the outcomes defined above, the data collected will include as much detail as possible to corroborate diagnosis, including but not limited, to histopathologic results, and relevant laboratory and imaging results. In addition, the following two outcome categories will be differentiated:

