- Reported outcomes: defined as all outcomes reported by physicians with no additional elements to corroborate the diagnosis;
- Confirmed outcomes: defined as all outcomes reported by physicians with any additional elements to corroborate the diagnosis such as histopathology for malignancies.

DMT after cladribine treatment: Sequential use of any DMT (immunosuppressive or immunomodulatory agents) after cladribine treatment in patients who experience a recurrence of the disease activity.

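### Section 9.10 names a possible detection bias towards cladribine, but no planned sensitivity analysis varies ascertainment for herpes zoster or severe infections

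*Protocol*

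**What the plan says.** Under information bias, Section 9.10 of the protocol says that "given that oral cladribine is a new drug, the treating physician might pay extra attention and evaluate the patient more frequently", "introducing a possible detection bias in comparison to patients treated with fingolimod". The paragraph ends there. The next bias discussed, channelling, is followed by a list of three measures.

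The only countermeasure to information bias is general: "instructions will be provided to all neurologists/physicians in the centers participating through the databases with additional primary data collection". For sources with secondary use only, the protocol says that "the data collection is based on routine clinical practice and cannot be influenced in the context of the study".

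Section 9.4.2 takes herpes zoster whatever its severity. It defines a severe infection by functional impairment and adds: "This definition includes serious and non-serious infections, in line with the definition used in the RMP of oral cladribine". It lists seriousness criteria, including death and hospitalisation. It also says that "the following two outcome categories will be differentiated", namely reported and confirmed, the latter being "defined as all outcomes reported by physicians with any additional elements to corroborate the diagnosis such as histopathology for malignancies".

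Section 9.8.3 makes zoster, tuberculosis, PML, other opportunistic infections and other severe infections primary categories beside malignancy. It lists seven sensitivity analyses: early malignancies excluded, as-treated exposure, on-treatment censoring, malignancy groupings, time since last dose, non-parametric cumulative incidence, and propensity-score adjustment.

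**The concern.** Events enter the database through contact with the treating physician. Section 9.2.5 has outcomes collected at routine visits, whose timing the protocol does not direct. In secondary-use sources it captures only what the physician thought worth recording. If one cohort is seen more often, more of its mild zoster and non-serious infections are recorded, and the rate ratio rises without any difference in risk.

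The seven sensitivity analyses vary lag, exposure, censoring, tumour grouping, model or covariate adjustment. All of them use the same recorded infections. Seriousness could show whether an excess is confined to events that depend on being seen, but it has no stated role in the comparison. An infection excess caused by closer observation could therefore not be recognised from the planned output. Nor could a genuine excess be defended against that explanation.

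**Working it through.** **1. Does any listed analysis vary ascertainment of infections?** Analyses 1 and 4 concern malignancy only. Analyses 2, 3 and 5 redefine exposure or censor follow-up. Analysis 6 changes the estimator and analysis 7 the adjustment. None restricts infections to serious, hospitalised or confirmed events. Visit counts are not a listed variable in Section 9.3. Section 9.4.2 describes lymphocyte-count frequency only for patients with severe lymphopenia, not as a comparison of cohorts.

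**2. Check of the method on the plan's own figure.** Table 4, Year 15, background 0.26 per 100 PY, true RR 1.3, 32,907 PY:
- Expected events are 0.0026 × 32,907 = 85.6 and 1.3 × 85.6 = 111.2.
- SE of the log ratio = √(1/85.6 + 1/111.2) = 0.144.
- P(lower limit > 1) = Φ(ln 1.3/0.144 − 1.96) = 45%; the table gives 46%.
- P(upper limit < 1.5) = Φ((ln 1.5 − ln 1.3)/0.144 − 1.96) = 17%; the table gives 17%.

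The normal approximation is adequate.

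**3. Person-years per cohort.** With 4,000 patients and 5% yearly loss after the first year (Section 9.6), ten years give 4,000 × [1 + (1 − 0.95⁹)/(−ln 0.95)] = 32,834, against 32,907 in the tables. Section 11.4 records AESI other than malignancy for 4 years, under rules written for the mixed-model sources. If that limit applied everywhere: 4,000 × [1 + (1 − 0.95³)/(−ln 0.95)] ≈ 15,100.

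**4. Zoster with no true difference.** Section 7 gives 0.86 per 100 PY on cladribine 3.5 mg/kg and 0.20 on placebo. No fingolimod rate is given, so each is tried in both cohorts. Capture of 90% on cladribine against 75% or 70% on fingolimod is assumed. The ratio is 0.90/0.75 = 1.20 or 0.90/0.70 = 1.29.

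At 0.86 and 32,907 PY there are 283 true events per cohort:
- 90% v 75%: 254.7 and 212.3 recorded; SE = 0.0929; Φ(0.1823/0.0929 − 1.96) = 50%.
- 90% v 70%: 254.7 and 198.1 recorded; SE = 0.0947; Φ(0.2513/0.0947 − 1.96) = 76%.

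The same formula gives P(lower 95% limit > 1):

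| Rate per 100 PY | PY per cohort | True events | 90% v 75% | 90% v 70% |
|---|---|---|---|---|
| 0.86 | 32,907 | 283 | 50% | 76% |
| 0.86 | 15,100 | 130 | 26% | 44% |
| 0.20 | 32,907 | 66 | 15% | 25% |
| 0.20 | 15,100 | 30 | 9% | 14% |

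Without bias the figure is 2.5%.

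**5. Severe infections.** Section 7 gives 0.84 per 100 PY on cladribine. Assume that half are non-serious and that serious events are fully captured. The ratio is (0.5 + 0.5 × 0.90)/(0.5 + 0.5 × 0.75) = 0.95/0.875 = 1.09, or 0.95/0.85 = 1.12. With 276 true events per cohort (32,907 PY) the chances are 15% and 24%; with 127 (15,100 PY) they are 9% and 13%.

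**The case against.** Section 9.8 is declared an overview with full detail left to the SAP, and disclosing a limitation without a dedicated analysis contradicts nothing. That is fair for operational detail. But the protocol itself enumerates its sensitivity analyses and attaches measures to channelling. The deferral covers the detail of the listed analyses and does not announce one on ascertainment.

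A reader might infer that the protocol expects closer surveillance, has no measure at all, never uses confirmation status, and so leaves every primary ratio uninterpretable. The text does not support this:
- It says might and possible, and gives no size.
- The physician instructions exist, although they do not address visit frequency and cover only the mixed-model sources.
- The primary malignancy definition already requires pathological confirmation, sensitivity analysis 1 drops cases in the first 6 and 12 months (for latency, not detection), and the Nordic cancer registers are listed with 100% coverage.
- For the other outcomes, reported and confirmed are to be differentiated, and the SAP may say how.

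It would also go too far to say that every planned sensitivity analysis must return the same spurious excess. Surveillance may change over follow-up, and analyses 3 and 5 weight periods differently. The net direction over ten years is not established.

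Two objections limit the remedy, and both stand. Confirmation requires only some corroborating element, which a closely tested patient is more likely to have, so a confirmed-only analysis can carry the same bias. And seriousness is a stated per-event field only in the mixed-model safety documentation (Section 11.4); Section 11.5 says secondary-use sources use no safety forms.

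**Conclusion.** The point holds for herpes zoster and severe infections. The protocol names a possible bias between cohorts in these primary comparisons, and no listed analysis could reveal it. Malignancy is less exposed, and the point does not extend to it with the same force.

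Under the assumed capture, zoster ratios of 1.20 to 1.29 would arise from detection alone. The chance of an interval wholly above 1 runs from 9% to 76%, depending on the background rate and on whether 4 or 10 years of recording apply. For severe infections the ratios are 1.09 to 1.12 and the chances 9% to 24%. Capture, its constancy over time, the non-serious share and the fingolimod rates are assumptions. The figures show what could happen and are not a forecast.

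**What to change.** Add to Section 9.8.3 a sensitivity analysis that repeats the adjusted rate ratios for zoster and for severe and opportunistic infections that led to hospitalisation or death. Run it where this is recorded or linkable: the mixed-model safety module, and the Nordic patient and cause-of-death registers, which Table 1 lists at 100% coverage and Section 9.5.1 says are linkable by personal identity number. Such events should depend much less on how often the neurologist sees the patient.

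State in Section 9.10 that an excess seen only in non-hospitalised events will be read as possibly due to detection. Treat a confirmed-only analysis as supportive at most. Summarise visit frequency by cohort only in sources that record visits.

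The primary analysis does not change. The cost is some model runs, with fewer events and wider intervals in this analysis alone. For example, if half of 276 severe infections per cohort qualified and every source contributed, the 95% limits at equal rates would widen from a factor of exp(1.96 × √(2/276)) = 1.18 to exp(1.96 × √(2/138)) = 1.27 either side. With only some sources contributing, they would be wider still.
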